### 1. BACKGROUND AND RATIONALE

The insertion of peripheral intravenous (IV) cannulas for the administration of medications, fluid and blood products is commonplace in hospitals today (1). Peripheral IV cannulas are minimally invasive and offer physicians and nurses the convenience of administering IV therapy as necessary (2). However, despite the many therapeutic benefits that IV cannulas offer, they can lead to complications such as infiltration, extravasation, bleeding, bruising, infection and phlebitis (2, 3). Of all the aforementioned complications, phlebitis is one of the most common and has been found to affect 5 to 75% of patients undergoing IV therapy in hospitals (4, 5).

Phlebitis refers to the inflammation of the venous tract and its surrounding tissues (5, 6). It can be caused by mechanical trauma, chemical irritation or infectious microorganisms (5, 7). Mechanical phlebitis results when the inserted IV cannula moves within the vein, causing friction and subsequently inflammation (8). Chemical phlebitis is caused by solutions that are hypertonic (osmolality > 500mOsm/litre) or are too acidic or alkali in nature (pH < 5 or pH > 9) (9). Infective phlebitis results when bacteria penetrate the vein, from the time of insertion or the initiation of IV therapy, and colonise the site, leading to inflammation and in serious cases, systemic sepsis (10).

The signs and symptoms associated with phlebitis include varying degrees of one or more of the following: erythema, pain, oedema, warmth, palpable venous cords, and purulent drainage (4). Using the VIP scale as modified by Jackson (4), the phlebitis grading can range from 0, indicating no signs of phlebitis, to 5, with symptoms of redness, pyrexia, a palpable venous cord and purulent drainage (4).

Although phlebitis is not a fatal diagnosis, it may cause permanent damage to the venous endothelium, thereby reducing the possibility of administering IV therapy via the damaged vein in future (11). It has also been found that patients diagnosed with phlebitis after their first IV cannula insertion were 5.1 times more likely to develop post-infusion phlebitis with subsequent cannulations (12). The development of phlebitis often leads to the early withdrawal and reinsertion of the peripheral IV cannula (6). It can cause a disruption in IV therapy, added stress and discomfort to patients, lengthened hospital stays (13), and an increase in healthcare costs (14). As such, the development of a protocol that aids in preventing the exacerbation and reducing the severity of phlebitis in hospitals, is of utmost importance.

While several topical and systemic therapies have been proposed in literature throughout the years, there is a lack of conclusive evidence on the optimal management of phlebitis in clinical practice (15). In all three causes of phlebitis (mechanical, chemical, infective), inflammation of the venous tract and its surrounding tissues will lead to the development and progression of phlebitis-related symptoms at the IV cannula site. As such, the use of anti-inflammatory agents in preventing and treating phlebitis have been widely studied and recommended (7, 16-18).

Oral and topical non-steroidal anti-inflammatory drugs (NSAIDs) have been found to be effective in the prevention (16, 17) and treatment of phlebitis (18, 19). Cokmez et al. (17) observed that the incidence of phlebitis was halved with the daily use of a topical NSAID gel at the cannula site (17). Similar findings were obtained in a study by Babaieasl et al. (16) where the use of topical Diclofenac, produced significantly lower incidences of phlebitis as compared to patients who received EMLA or a placebo. In another study,

both topical and oral Diclofenac were found to be more effective in improving the clinical signs and symptoms of phlebitis when compared against patients who received no intervention (18).

Local inflammation and septicaemia at IV cannula sites have also been found to be correlated with positive cultures of the IV cannulas post removal (17, 20). This is largely attributed to poor practices during IV cannula insertion and drug administration, which increase the risk of bacteria introduction into the vein (10, 16, 21). The use of topical antibiotic and antiseptic agents have thus been advocated for the treatment of phlebitis (22). Antibiotics are however not recommended for local wound therapy, because of limitations in effectiveness and the potential contribution to the formation of antibiotic-resistant strains (23). Antiseptic or plant-based agents like iodine and sesame oil, on the contrary, possess broad spectrum antimicrobial effects, are effective on biofilms, possess anti-inflammatory properties and promote wound healing, without any risk of contributing to bacterial resistance (10, 23, 24, 25, 26).

To date, there have been three studies conducted to evaluate the effectiveness of Povidone-iodine in preventing phlebitis (27-29). In 1980, Noble et al. (27) tested the effectiveness of a daily Povidone-iodine 0.5% dry powder application at IV cannula sites, in reducing phlebitis. Two studies by Thompson et al (28, 29) likewise studied the effectiveness of Povidone-iodine at preventing phlebitis at IV cannula sites, when applied once immediately upon insertion. All three studies (27, 28, 29) found that iodine was not effective in preventing the incidence of phlebitis or reducing the incidence of cannula colonisation (27).

## 2. HYPOTHESIS AND OBJECTIVES

#### Hypothesis:

The application of topical sesame oil will be effective at preventing phlebitis at peripheral IV cannula sites in adult patients within the cardiovascular and cardiothoracic department of a tertiary hospital.

#### Aim of study:

• To determine the effectiveness of topical sesame oil in preventing phlebitis at peripheral IV cannula sites in adult patients within a cardiovascular and cardiothoracic department of a tertiary hospital.

#### **Objectives:**

• To measure the incidence and severity of phlebitis at 12 hour intervals, at peripheral IV cannula sites, in adult patients within a cardiovascular and cardiothoracic department of a tertiary hospital.

• To measure the incidence and severity of phlebitis 12 hourly for up to 24 hours post IV cannula removal.

• To compare the incidence and severity of phlebitis at 12 hour intervals, between patients who received topical sesame oil and patients who received topical liquid paraffin oil at the IV cannula site, in adult patients within a cardiovascular and cardiothoracic department of a tertiary hospital.

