#### 4. STUDY POPULATION

#### 4.1. List the number and nature of subjects to be enrolled.

650 adult patients between the age of 21 to 80, and from inpatient wards within The National Heart Centre of Singapore will be recruited, regardless of ethnicity or gender.

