#### 4.3. Inclusion Criteria

- Age 21-80
- Patients must speak and understand either English or Mandarin
- Patients who possess a peripheral IV cannula
- IV cannula must have been inserted for less than 12 hours
- IV cannula must be on an upper extremity
- IV cannula must be patent
- IV cannula sites must show no signs of redness, swelling, pain, a palpable venous cord or pyrexia
- Patient must be admitted to a cardiology ward in the National Heart Centre Singapore

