Demographic and clinical data will be recorded into a table. The patient will be instructed not to wash or wipe the topical agent off. The time and date of the start of treatment applied and subsequent treatments at 12 hour intervals will be documented. At the start of the study and at each 12 hour interval, the investigator will observe for signs of phlebitis using the Visual Infusion Phlebitis scoring tool [Appendix 2], before application of the next treatment. The study investigators will be the only ones applying the treatment/control and completing the data collection form [Appendix 3] every 12 hours. Patient identifiers (name and NRIC) will be verified before every application of the treatment/control and the completion of the data collection form.

Application of the treatment or control will be made every 12 hours for up to 72 hours, where the IV cannula will then be removed according to hospital guidelines. The IV cannula site will be observed, every 12 hours for up to 24 hours post IV cannula removal, for phlebitis or complications.

Patients will be withdrawn from the study the moment they show signs of adverse reactions from the topical treatment or control.

Participants will be involved in the study for a maximum of 96 hours. If the IV cannula is removed accidentally or not due to phlebitis before the 72-hour period is up, re-insertion of a new cannula and re-application of oils will not be done on a new site. The patient's IV cannula site will continue to be observed for 24 hours at 12-hour intervals after cannula removal. The partial data will be kept and analysed. If the patient is discharged before the 96 hour observation period is up, the 24 hour post-removal observation will continue to be carried out at 12 hour intervals, via phone call or video call. The patients' phone numbers will be obtained during the informed consent process, only for follow up purposes.

The application of either sesame oil or liquid paraffin oil is not part of the routine procedures or standard of care in the ward, and will only be applied for the purpose of this research. Both the sesame oil and liquid paraffin oil are marketed products and will be used as per label.

The study is estimated to continue for two years, commencing in February 2022 and ending in December 2023.

At no point of the study will any audio or video recording take place.

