### 8. SAMPLE SIZE AND STATISTICAL METHODS

#### 8.1. Determination of Sample Size

Using a power analysis of 20% and a difference of 35%, a sample size of 44 participants is required if subgroup analysis is not required. We then rounded it up to 100 to account for an attrition rate of 5%.

Data will be analysed with the Statistical Package for Social Science (SPSS) software program (v. 28) using descriptive statistics such as relative and absolute frequencies, mean and standard deviation, and inferential statistics such as Chi-square, independent t-test and Hazard ratio.

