#### 8.2. Statistical and Analytical Plans

#### a. General Considerations

The distribution and dispersion of the data will be examined through descriptive numerical summaries and graphical tools such as scatter plots, via SPSS. The data will then be analysed using descriptive statistics such as relative and absolute frequencies, mean and standard deviation, and inferential statistics such as Chi-square, independent t-test and Hazard ratio.

As missing data can potentially spoil or invalidate a study, we will spare no effort in minimising incomplete or missing data. All data will be carefully inspected to identify missing items and outliers. In the analysis of incomplete data, we will consult with a biostatistician regarding the use of incomplete-data analysis strategies that will allow us to utilise the available information effectively.

b. Safety Analyses

All adverse events, such as the development of allergic reactions to the oils, leading to the participant's withdrawal from the study will be collected and tabulated. Incidences and severity of phlebitis experienced during the course of the study will also be collected and tabulated. All adverse reactions and phlebitis incidences will be tabulated for both the treatment and control group. The extent and severity of symptoms will also be documented. For phlebitis incidences, the severity will be assessed with the Visual Infusion Phlebitis (VIP) scoring tool [Appendix 2]. The number of adverse reactions will be summarised for both the treatment and control group. Frequency counts and percentages will be calculated and reported.

c. Interim Analyses

We will compare treatment groups on descriptive and clinical characteristics at baseline to ensure that randomisation has succeeded. SPSS will be used for group comparisons, descriptive calculations and conditional regression modelling. We will examine the distributions of all important variables at baseline and at the end of the data collection period, to assess for covariate imbalance. Formal statistical methods to test for selection bias will be used.

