#### Visual Infusion Phlebitis Scoring Tool

# **Visual Infusion Phlebitis Scoring Tool**

IV site appears healthy	0	No signs of phlebitis OBSERVE CANNULA
One of the following signs is evident: • Slight pain near IV site OR • Slight redness near IV site	1	Possible first signs of phlebitis RESITE CANNULA
Two       of the following are evident:         •       Pain at IV site         •       Redness         •       Swelling	2	Early stage of phlebitis RESITE CANNULA
All of the following signs are evident: • Pain at IV site • Redness • Swelling	3	Medium stage of phlebitis INITIATE TREATMENT RESITE CANNULA

 
All of the following signs are evident and extensive:
 
Pain at IV site
 
Redness
 
Swelling
 
Palpable venous cord
 
	4	Advanced stage of phlebitis or start of thrombophlebitis INITIATE TREATMENT RESITE CANNULA
All of the following signs are evident and extensive: 
 
Pain at IV site
 
Redness
 
Swelling
 
Palpable venous cord
 
Pyrexia
 
	5	Advanced stage of thrombophlebitis INITIATE TREATMENT RESITE CANNULA

Tool Developed by Andrew Jackson – Consultant Nurse Intravenous Therapy & Care, The Botherham NHS Foundation

This tool was modified for use in this study.

Right arm	Left arm	Participant No:	
		Age:	
		Gender: Male / Female Race:	
		Medications	
		Oral / IV anticoagulants (if any):	
		IV Insertion	
		 Date: Time:	
		Size:	
		Site: Inserted at :(Dept)	
		IV Removal	
Mark IV Conn	Date: Time:		
Mark IV Cann	Reason:		

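### Phlebitis is to be compared every 12 hours on two outcomes, but no primary endpoint, VIP cut-off for analysis, alpha or multiplicity rule is named, so the main claim has no fixed error rate

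*Combined protocol and SAP*

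**What the plan says.** Section 2 (Objectives) has three bullets. Two concern measurement, including "To measure the incidence and severity of phlebitis 12 hourly for up to 24 hours post IV cannula removal". The third is the only comparison between arms: "To compare the incidence and severity of phlebitis at 12 hour intervals, between patients who received topical sesame oil" and patients given liquid paraffin oil. It covers two outcomes, incidence and severity, and gives no order of importance. The hypothesis and aim in the same section speak only of preventing phlebitis.

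The data collection form has columns at 12, 24, 36, 48, 60 and 72 hours, then 12 and 24 hours after removal.

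Sections 8.1 and 8.2(a) both list "inferential statistics such as Chi-square, independent t-test and Hazard ratio". None is linked to an outcome, a time point or a primary role. Section 8.1 begins "Using a power analysis of 20% and a difference of 35" (that is, 35%) and arrives at 44 participants. It gives no significance level, control rate, outcome or time point for that difference.

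Appendix 2 grades the site from 0 to 5. Score 1 reads "Possible first signs of phlebitis RESITE CANNULA"; score 2 is labelled an early stage. No passage says which score makes a patient a case in the analysis.

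Section 8.2(b), under safety, tabulates phlebitis over the whole study by arm, as counts and percentages. It specifies no test.

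**The concern.** A trial claim has a known error rate only if the test behind it is fixed beforehand. Here three choices are open at once: the assessment, the VIP cut-off and the test. A result could be called positive from a chi-square at 36 hours on score 1 or above, a t-test of scores at 72 hours, or a hazard ratio with a different case definition. Nothing in the plan would rank one above another.

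The plan also does not say how a case is counted at later assessments. The patient may stay a case (cumulative counting) or drop out of the denominator. These are different comparisons with different error rates.

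The sample size suffers as well. A difference of 35% cannot be tied to an analysis that has not been named.

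**Working it through.** **1. The plan's own figure.** The required number per arm for two proportions (pooled variance under the null) is

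n = [z(α/2)·√(2p̄(1−p̄)) + z(β)·√(p1(1−p1) + p2(1−p2))]² / (p1−p2)².

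Section 8.1 gives neither the rates nor alpha. Section 1 cites a study with an eightfold ratio. An eightfold ratio with a 35-point gap means c − c/8 = 0.35, so c = 0.40, that is 40% against 5%. Take two-sided 5% and read the 20% as beta:

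- p̄ = 0.225; 1.960 × √0.34875 = 1.157; 0.842 × √0.2875 = 0.451.
- n = (1.157 + 0.451)² / 0.1225 = 21.1, so 22 per arm and 44 in total.

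The 44 is reproduced, but only by supplying an alpha and two rates that the section does not state. Other control rates with the same gap give 27 to 31 per arm. The figure therefore does not identify the endpoint.

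**2. Reference values if tests were independent.** With k tests at 5%, the chance of at least one false positive is 1 − 0.95^k: 26.5% for k = 6 and 33.7% for k = 8.

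**3. Simulation under no treatment effect.** Inputs from the documents:
- 44 and 100 participants (Section 8.1); "650 adult patients between the age of 21 to 80" (Section 4.1)
- six or eight assessments (data collection form)
- background incidence of 5 to 75% (Section 1)

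Assumptions not in the documents:
- 1:1 allocation and two-sided 5% at every assessment
- uncorrected Pearson chi-square
- constant hazard per interval
- in the last three rows and the 100-participant, 10% row, removal for other reasons in 0 to 20% per 12 hours

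The table shows the chance of at least one false positive on incidence alone (six / eight assessments).

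| Participants | Incidence | Cumulative counts | Cases leave denominator |
|---|---|---|---|
| 44 | 5% | 1% / 2% | near 0 |
| 44 | 10% | 4% / 7% | near 0 |
| 100 | 5% | 5.5% / 7.8% | near 0 |
| 100 | 10% | 10–12% / 12–14% | 2% / 3–4% |
| 100 | 22% | 14–16% / 16–18% | 12–14% / 16–18% |
| 100 | 44–73% | 15–18% / 17–21% | 20–28% / 27–34.5% |
| 650 | 10–73% | 13–17% / 15–20% | 22–27% / 29–34% |

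If events cluster late, cumulative counting at eight assessments reaches about 24–27%. The top of the last column is the independent-test value of 33.7% within simulation error (at most 0.8 points).

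**4. Cut-off choice alone.** With one per-patient test and a free choice among VIP cut-offs of 1, 2 or 3 and above, the false-positive risk is 7–14%, depending on the assumed severity split and event rate. The problem thus remains even without visit-by-visit testing.

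**5. One pre-specified test.** A single per-patient chi-square gives 4.4–5.9% and a single log-rank test 4.4–5.8%, which is the nominal level within simulation error.

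**The case against.** The plan nowhere says that each assessment will be tested at 5%. The objective can be read as describing the measurement schedule. The hypothesis and aim name one idea, Section 8.1 gives one difference, and the listed hazard ratio is a single comparison over all follow-up. Section 8.2(b) already tabulates phlebitis over the whole study by arm, which favours a per-patient reading. When events are sparse, repeated testing hardly inflates the error at all.

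Most of this stands, and it limits the numbers. A reader might infer that the trial will run a dozen or more tests at 5%, and so carries a false-positive risk of one in three or worse. The documents do not support that: no such testing scheme is stated. A reader might also infer that cases leave the denominator, so that later assessments no longer compare the randomised groups. No passage describes that denominator. Section 5 keeps partial data and continues observation after removal, which points the other way.

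What the objection does not supply is a choice. The hazard ratio is not made primary and its event is undefined. The whole-study tabulation is descriptive and sits under safety. One difference without an outcome, cut-off or alpha does not fix a test.

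**Conclusion.** The omission is confirmed: the documents contain no primary endpoint, no VIP cut-off for analysis, no alpha and no multiplicity rule, while the only comparative objective covers two outcomes at six to eight assessments. As written, the error rate of the main claim is not fixed.

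The size of the inflation is conditional. If each assessment were tested at 5%, the risk for incidence alone runs from none (about 5% incidence, 44 to 100 participants) to roughly 15–25% on cumulative counts when events are not sparse. It rises to about one in three only on the unstated reading that cases leave the denominator. These figures rest on assumed alpha, allocation, hazard shape and removal rates; the omission does not. It should be corrected before outcomes are compared by arm.

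**What to change.** In Sections 2 and 8.2, name one primary analysis, tested once at two-sided 5%: phlebitis per patient (yes or no) over the whole observation period, in all randomised patients. Fix one VIP cut-off before outcomes are compared by arm, for analysis only and without bearing on care of the cannula. State that a case remains a case after removal. This agrees with the whole-study tabulation already in Section 8.2(b).

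Make the hazard ratio for time from first application to first phlebitis supportive, or make it primary and the proportion supportive, if that is decided in advance. Compare severity once, on each patient's highest VIP score, as a secondary analysis. Report 12-hourly results descriptively. Restate Section 8.1 for the chosen endpoint, with its alpha, power and control rate.

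The cost is wording in Sections 2 and 8; no visits are added. At a 35-point difference with 50 per arm, a single per-patient chi-square has 95–99% power by formula (for 40 against 5%, 60 against 25%, 67.5 against 32.5% and 78 against 43%). What is given up is any claim of significance at an individual assessment. Keeping such claims for incidence would need, for example, a Bonferroni level of 0.05/6 = 0.0083 or 0.05/8 = 0.00625 per test.

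### The 12-hourly comparison has no stated denominator, and from about 48 h a comparison of recorded scores is between groups selected by outcome rather than the randomised groups

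*Combined protocol and SAP*

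**What the plan says.** - **Comparison.** Section 2, third objective: "To compare the incidence and severity of phlebitis at 12 hour intervals, between patients who received topical sesame oil" and those who received liquid paraffin oil. It is the only comparative objective. It does not say whether incidence means new cases among cannulas in place, positive scores among sites still observed, or cases to date among all randomised patients.
- **What a positive score triggers.** The modified Visual Infusion Phlebitis (VIP) tool in Appendix 2 reads, at score 1: "Possible first signs of phlebitis RESITE CANNULA". Every higher score also carries the re-site instruction.
- **Follow-up.** Section 5: "Application of the treatment or control will be made every 12 hours for up to 72 hours", and "The IV cannula site will be observed, every 12 hours for up to 24 hours post IV cannula removal, for phlebitis or complications". The data collection form matches this, with VIP cells from 0 to 72 h and at 12 and 24 h after removal.
- **Early removal.** Section 5 covers one case: "If the IV cannula is removed accidentally or not due to phlebitis before the 72-hour period is up". Then "re-insertion of a new cannula and re-application of oils will not be done on a new site", the site is observed for a further 24 h, and "The partial data will be kept and analysed". There is no corresponding analysis rule for removal because of phlebitis.
- **Methods.** Sections 8.1 and 8.2 list chi-square, t-test and hazard ratio without defining the event, time origin or censoring. Methods for incomplete data are left to later consultation with a biostatistician.

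**The concern.** The outcome decides who is still being scored. A site with phlebitis at 24 h is re-sited, scored at 36 and 48 h, and has no score at 60 or 72 h. If the oil works, more control sites leave in this way, so the later columns of the form hold differently selected groups in the two arms. Even a single later-interval comparison is affected, whatever the number of intervals tested.

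A preventive effect that is constant over time could then appear to fade with dwell time, and the late absolute difference could look small although many more control patients have had phlebitis. Severity is exposed as well: after re-siting at score 1, the score is followed for only 24 h in either arm.

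**Working it through.** The plan gives no figure for this selection, so there is none to reproduce. The check has three steps.

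**1. Who has a score, and when.** Take removal at the scheduled assessment that finds a score of 1 or more. Phlebitis found at time t is scored at t + 12 and t + 24 h, then no more. A case at 12 h is still scored at 24 and 36 h and first missing at 48 h. At 72 h, cases from 12, 24 and 36 h have no score. Removals between assessments could shift this slightly, hence about 48 h.

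**2. Unequal risk (all rates assumed).** Six 12-hour intervals; 30% of sites have a 30% risk per interval and 70% have 2%; sesame oil halves both. Signs are taken to persist for the 24 h after removal. Let f = 1 for control and 0.5 for sesame. After k intervals the share still in place is

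S(k) = 0.30(1 − 0.30f)^k + 0.70(1 − 0.02f)^k.

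New cases in interval k are S(k−1) − S(k). The in-place risk divides these by S(k−1). The observed-site proportion at interval k (k ≥ 3) is [S(k−3) − S(k)] / S(k−3). Cumulative incidence is 1 − S(k).

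At 72 h (k = 6):
- In place at the start of the interval, control: 0.30 × 0.70^5 + 0.70 × 0.98^5 = 0.0504 + 0.6327 = 0.6832, of which 7.4% are high-risk. Risk = (0.0504 × 0.30 + 0.6327 × 0.02) / 0.6832 = 4.07%.
- The same for sesame: 0.30 × 0.85^5 + 0.70 × 0.99^5 = 0.1331 + 0.6657 = 0.7988, of which 16.7% are high-risk. Risk = (0.1331 × 0.15 + 0.6657 × 0.01) / 0.7988 = 3.33%. Ratio 0.82.
- Cumulative: control 1 − 0.0353 − 0.6201 = 34.5%; sesame 1 − 0.1131 − 0.6590 = 22.8%. Ratio 0.66.
- Observed sites: control (0.7617 − 0.6554) / 0.7617 = 14.0%; sesame (0.8634 − 0.7722) / 0.8634 = 10.6%.

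| Time | New cases / cannulas in place (RR) | Positive / sites still observed (RR; difference) | Cases to date / all randomised (RR; difference) |
|---|---|---|---|
| 12 h | 10.4% v 5.2% (0.50) | 10.4% v 5.2% (0.50; 5.2 points) | 10.4% v 5.2% (0.50; 5.2 points) |
| 36 h | 7.0% v 4.4% (0.62) | 23.8% v 13.7% (0.57; 10.2) | 23.8% v 13.7% (0.57; 10.2) |
| 72 h | 4.1% v 3.3% (0.82) | 14.0% v 10.6% (0.76; 3.4) | 34.5% v 22.8% (0.66; 11.7) |

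The last two columns agree up to 36 h and separate from 48 h, as step 1 implies. With a high-risk rate of 20% instead of 30%, the 72 h ratio is 0.65 in place and 0.60 cumulatively (30.1% v 18.2%).

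**3. Equal risk.** Take 72 h incidence of 78% v 43%: the control rate of the amiodarone study cited in section 1, less the 35-point difference in section 8.1. The per-interval risks are 1 − 0.22^(1/6) = 22.3% and 1 − 0.57^(1/6) = 8.9%.
- In-place ratio: 0.40 at every interval, with no drift.
- Observed sites at 72 h: 1 − 0.777^3 = 53% v 1 − 0.911^3 = 25%. The ratio is 0.46 and the difference 29 points.
- Cumulative: ratio 0.55, difference 35 points.
- Still in place at the start of the last interval: 28% v 63%.

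So under equal risk the absolute difference among observed sites shrinks, but the ratio is not diluted. Adding gamma-distributed risk between patients (variance 1) to 78% v 43% moves the in-place ratio from 0.30 at 12 h to 0.55 at 72 h. At an assumed 30% v 15% it moves only from 0.43 to 0.50.

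**The case against.** The strongest reply is that the plan is undefined here rather than biased. The objective fixes no denominator and could be read as cumulative incidence over all randomised patients. A hazard ratio is already listed, and the first score of 1 or more is recorded before the site leaves observation, so time to first phlebitis is not truncated by re-siting. Partial data are kept. The documents name no primary time, so nothing shows that the trial reads out at 60 to 72 h. The cumulative ratio also drifts in the example (0.50 to 0.66), and under milder inputs the two measures are close.

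Most of this stands, and it limits the claim. Three stronger readings are not supported:
- A reader might infer that only surviving cannulas are compared. Removed sites are still scored for 24 h.
- A reader might infer that the randomised comparison is lost from the second interval. Phlebitis cases found at scheduled assessments leave from 48 h at the earliest.
- A reader might infer that any preventive effect is understated. Dilution of the in-place ratio needs unequal risk between patients.

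The reply does not remove the gap. Nothing in the plan selects the cumulative reading or defines the hazard ratio, and the form, analysed column by column as the objective is worded, gives the selected comparison.

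**Conclusion.** The concern holds in a limited form. From about 48 h, a comparison of recorded scores is between groups selected by outcome. The later absolute difference can be understated: 3.4 against 11.7 points at 72 h in the unequal-risk example, and 29 against 35 points under equal risk at 78% v 43%. Drift of the in-place ratio towards 1 is conditional on unequal risk. That condition is plausible, since section 1 names mechanical, chemical and infective causes, but the documents do not quantify it. The drift ranges from small (0.43 to 0.50) to marked (0.50 to 0.82) across the assumptions tried. The effect on the severity contrast cannot be signed from the documents.

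The rates, the spread of risk and the persistence of signs for 24 h are assumptions. Loss through accidental removal or discharge was not modelled. The change is worth making because it replaces a selected comparison with a randomised one using data already collected.

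**What to change.** Change the analysis wording only, in sections 2 and 8.2:
1. Restate the third objective as the cumulative proportion of all randomised patients with a first VIP score at or above a stated threshold by each 12-hour mark, carrying events forward. Name one time as primary. If the threshold is above 1, say how sites re-sited at a lower score are counted, since they are followed for only 24 h more.
2. Define the listed hazard ratio as time to first phlebitis, with time origin and event stated. Censor removals for other reasons at the end of their 24 h follow-up. Add a cumulative incidence analysis with such removal as a competing event, as a sensitivity analysis.
3. Compare severity as the worst score per patient.
4. Show the 12-hourly tables among sites still observed as descriptive only, with the number at risk in each arm.

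The cost is a few sentences. No new data are needed and clinical management is unchanged. The small downside is that interval-specific p-values among observed sites are no longer inferential.
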